Specific Aims: This study will attempt to determine if it is possible to reduce the post-operative opioid requirements for patients undergoing laparoscopic gastric bypass surgery while still providing acceptable levels of pain relief by utilizing an intra-operative infusion of ketamine. This study will compare two groups of patients presenting for gastric bypass surgery. The two groups will be randomized to a control group who will receive a standard, narcotic based pain relief anesthetic and the study group which will receive an intra operative ketamine infusion. After the surgery the patients’ narcotic use and pain scores will be followed for 48 hours to determine if the intra operative ketamine infusion is effective at decreasing post-operative narcotic requirements.

Research Plan: The study will be a head to head experiment with one group receiving narcotic medication during the surgery and the other group receiving a ketamine infusion. Both groups will receive 2 mg of versed on the way from pre op holding to the operating room, which is standard practice.

We plan to enroll at least 48 patients in this study, with 10 additional patients in case patients are removed from the study for any reason. This number was arrived at by a power analysis performed by [name] last year and it was estimated that to see a 30% reduction in narcotic use we would need two groups of 24, emphasizing that this would be a pilot study. The study by Fu utilized two groups of twenty participants each and found that “cumulative morphine consumption on D1 and D2 was reduced by approximately 40%”.⁷ The surgeon, [name], performs between three and five laparoscopic gastric bypasses per week so this number of patients should be able to be enrolled in a reasonable amount of time.

The ketamine group will receive 100 mcg of fentanyl at induction of anesthesia and then no further narcotics during the surgery. During induction the patient will receive a 20 mg bolus of ketamine, a dose of propofol deemed appropriate by the anesthesia team to render the patient unconscious and a dose of neuromuscular blocking medication followed by an intraoperative infusion of ketamine at 5 mcg/kg/min beginning after induction, and ending at the beginning of wound closure.

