The narcotic group will receive no ketamine but rather a more standard anesthetic consisting of 100 mcg of fentanyl, a dose of propofol deemed appropriate by the anesthesia team to render the patient unconscious and a dose of neuromuscular blocking medication for induction. Intraoperatively only the narcotic group will be given intraoperative boluses of fentanyl and 0.3 mg of hydromorphone approximately 45 minutes prior to the end of surgery.

Both groups will receive 1 gram of Ofirmev (acetaminophen) infused over 15 minutes starting when wound closure begins. They will also both receive neuromuscular blockade reversal medication and a dose of Zofran at the end of the surgery. These medications are routine for this surgery. Anesthesia providers will be allowed to provide other non-analgesic medications to the patient which is consistent with their usual practice.

The amount of narcotics a patient receives is part of the medical record. Beginning in the PACU amount of narcotics needed to control the patient’s pain (converted to morphine equivalent units) and pain scores (a hospital standard measure) will be collected for 48 hours for the study, or until discharge, whichever occurs sooner. The conversion to a morphine equivalent unit is to allow us to compare different narcotics the patient may receive in a more standardized way. The results will be analyzed and compared between the two groups.

Patients will be eligible for inclusion in this study if they are between 18 and 65 years old presenting for laparoscopic gastric bypass surgery at Shands Hospital.

Patients would be excluded if they are below 18 or older than 65 or have hypersensitivity, allergy, or contraindications to fentanyl, propofol, hydromorphone or ketamine; the medications which could be administered in this study. Patients with cardiovascular disease who cannot tolerate the sympathomimetic effects of ketamine and ASA 4 patients will be excluded from this study.

Participants for this study will be recruited by [name] in his surgical clinic. If they are going to require gastric bypass surgery they will be informed of the study and asked to participate. The patients will be randomized into the two treatment groups utilizing a computer generated block randomization to get groups of equal size in each treatment. There will be 9 blocks of 6 and 1 block of 4 in order to evenly divide the 58 patients.

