Patients PHI will be accessed by the study staff in collecting the data and clinicians in providing care to the patients. The only data which will be recorded will be pain scores and narcotic usage during the 48 hours after surgery. Consent for participation in the study will be scanned into the patient's record. Hard copies of the data will be saved in a locked drawer in [name] lock office until converted into a digital format, consistent with the department's protocol. The data will be analyzed with the help of the anesthesia departments statistical consultant.

Possible Discomforts and Risks: The patients will be undergoing gastric bypass surgery which, by its nature, is painful. They will be given FDA approved medications, consistent with their labeling, during the operation to minimize that pain. Post operatively the patients will be given whatever medications they need to control their pain. The largest potential side effects of ketamine is vivid dreams which may be unpleasant, this side effect should be blunted or avoided by the pre-operative administration of versed. As ketamine is a standard anesthetic drug, in the event of a temporary state of confusion or agitation related to ketamine the PACU would do as they do with any patient who has this reaction to ketamine and dim the lights and draw the curtains, allowing the patient to remain calmer as they wake from anesthesia. If the emergence is too distressing an additional dose of versed may be administered to blunt the reaction.

Possible Benefits: The patients could experience satisfactory pain relief while using less narcotics a goal recommended by the ASA. In receiving less narcotics the patients should have a lower incidence of negative side effects of narcotics including respiratory depression. The benefit to future patients will be if we are able to show that we can both decrease use of post-operative narcotics while maintaining satisfactory pain relief we can utilize this as a standard anesthetic regimen and avoid some of the negative and dangerous side effects of narcotics.

Conflict of Interest: Neither I nor the study team have any conflicts of interest involved in this study.

Bibliography:

1. Cdc.gov. Adult Obesity Facts | Data | Adult | Obesity | DNPAO | CDC. 2015. Available at: <http://www.cdc.gov/obesity/data/adult.html>. Accessed June 25, 2015.

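### The recorded-data rule leaves out pre-operative opioid use, so the narcotic comparison cannot be adjusted for it or shown to be balanced on it; the cost is precision, not validity

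*Protocol*

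**What the plan says.** All of the relevant text is in the protocol's Research Plan.

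- **Data.** The paragraph on health information and data storage says: "The only data which will be recorded will be pain scores and narcotic usage during the 48 hours after surgery". No other part of the protocol provides for a baseline item.
- **Inclusion.** "Patients will be eligible for inclusion in this study if they are between 18 and 65 years old presenting for laparoscopic gastric bypass surgery" (at the named hospital).
- **Exclusion.** Age outside that range; "hypersensitivity, allergy, or contraindications to fentanyl, propofol, hydromorphone or ketamine; the medications which could be administered in this study"; and "Patients with cardiovascular disease who cannot tolerate the sympathomimetic effects of ketamine and ASA 4 patients will be excluded from this study". Prior or chronic opioid use is not mentioned.
- **Allocation.** Computer-generated blocks, nine of 6 and one of 4, for 58 patients. No stratification factor is stated.
- **Outcome.** Narcotic use from the PACU onward, in morphine equivalents, for 48 hours or until discharge if that is sooner.
- **Size.** "it was estimated that to see a 30% reduction in narcotic use we would need two groups of 24", and "We plan to enroll at least 48 patients in this study, with 10 additional patients in case patients are removed". The standard deviation, significance level and power behind the 24 are not given.

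**The concern.** The outcome is how much opioid a patient needs after surgery, and the protocol gives post-operative analgesia according to need. How much opioid the patient took before surgery is the natural baseline for that quantity. It is reasonable to expect it to predict the outcome, although the documents do not say how strongly.

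Choosing covariates is normally a matter for the analysis plan, and leaving that open would be no fault. Here the protocol goes further: it closes the list of recorded data. An analysis plan can only adjust for, or tabulate, what has been collected. If some enrolled patients are opioid users, two things are lost: the precision that adjustment would give, and the reader's ability to check whether such patients fell unevenly between two small arms.

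**Working it through.** **1. The plan's own figures.** Enrolment is consistent: 9 × 6 + 4 = 58 = 48 + 10. The 24 per group cannot be confirmed, because its inputs are not stated. Solving backwards with an assumed two-sided 5% level and 80% power, n = 2(1.96 + 0.84)²·CV²/0.30² = 24 gives CV (SD divided by control mean) = 0.371. The noncentral t gives 0.363. This is possible, so the figure is not refuted either.

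**2. Illustrative model.** None of these inputs is in the documents.

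- A proportion p of patients use opioids before surgery.
- Non-users have mean consumption 1 and users have mean r.
- The CV is 0.4 within each stratum.
- The effect is 30% of the overall mean, with the same variance in both arms, a two-sided 5% test and n = 24 per arm.

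Formulas:

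- overall mean μ = 1 − p + p·r
- within-stratum variance W = 0.16·(1 − p + p·r²)
- between-stratum variance B = p(1 − p)(r − 1)²
- share of variance explained by baseline use = B/(W + B)
- power from the noncentral t with 46 degrees of freedom, standardized effect 0.3μ/√(W + B) unadjusted and 0.3μ/√W adjusted
- shift in the difference from three extra users in one arm = (3/24)(r − 1)/μ, as a fraction of the mean

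Example, p = 0.10 and r = 2: μ = 1.10, W = 0.16 × 1.30 = 0.208 and B = 0.09 × 1 = 0.09. The share is 0.09/0.298 = 30%. The total CV is √0.298/1.10 = 0.496, giving power 54%. The adjusted CV is √0.208/1.10 = 0.415, giving power 69%.

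| p | r | Share explained | Power unadjusted | Power adjusted | Shift from 3 extra users |
|---|---|---|---|---|---|
| 5% | 1.5 | 6.5% | 68.6% | 71.5% | 6.1% |
| 5% | 2 | 20.5% | 60.3% | 70.2% | 11.9% |
| 5% | 2.5 | 34.6% | 50.3% | 68.2% | 17.4% |
| 10% | 1.5 | 11.1% | 66.1% | 71.2% | 6.0% |
| 10% | 2 | 30.2% | 53.6% | 68.9% | 11.4% |
| 10% | 2.5 | 45.4% | 41.7% | 65.9% | 16.3% |
| 20% | 1.5 | 16.7% | 62.7% | 70.6% | 5.7% |
| 20% | 2 | 38.5% | 47.3% | 67.5% | 10.4% |
| 20% | 2.5 | 52.3% | 35.8% | 63.7% | 14.4% |

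With no opioid users (CV 0.4 throughout), power is 72.0%. That is the reference point, not 80%.

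**3. Chance imbalance.** Take the number of users in each arm as independent Binomial(24, p). A difference of three or more, in either direction, has probability 9% at p = 5%, 22% at p = 10% and 36% at p = 20%. In any one direction it is half of that: 5%, 11% and 18%.

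**4. If all 58 complete (29 per arm).** Over the same grid, power is 42-77% unadjusted and 72-80% adjusted, with 80% if there are no users. The ten extra patients reduce the loss but do not remove it.

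**5. Validity.** Simulating the unadjusted t-test with no treatment effect (100,000 trials per setting) gives type I error of 5.0%, 4.7% and 4.9% at (5%, 1.5), (10%, 2) and (20%, 2.5). The test holds its level.

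**6. If the planning SD already included opioid users.** Unadjusted power is then the assumed 80%. A baseline covariate explaining 10%, 20%, 30% or 40% of the variance would raise it to 84%, 88%, 92% or 95%.

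**The case against.** *The sentence is not a dataset specification.* It stands in a paragraph on access to health information and storage of paper copies. Taken literally, it would also bar recording the allocated arm and the discharge time, without which the planned comparison could not be made. This shows that the sentence is loosely drafted. It does not supply the missing item, because nothing else in the protocol provides for any baseline variable.

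*The information can be retrieved.* This is right as far as it goes. Study staff have access to the record, and prior opioid use is a baseline fact. A reader might infer that adjustment is ruled out for good. The documents do not support that: a wording change would permit it. They do not permit it as they stand.

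*Randomization deals with imbalance.* This stands. A reader might infer that uneven numbers of opioid users would bias the trial or produce false positives. They would not: chance imbalance is already in the standard error, and step 5 shows the error rate is kept. What remains is lost precision, and an imbalance that could be neither seen nor ruled out in the one trial that is run.

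*The size is speculative.* This also stands. The protocol gives no prevalence, no ratio of need and no SD. It is silent on opioid users; it does not say that it expects them. In the mildest setting the gain is only about 3 points of power. Reading the low figures as the trial's actual power would also be wrong, since a CV of 0.4 alone brings power down to 72%.

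*It is a pilot.* The protocol does call it one, but it still sizes the trial on a 30% reduction and foresees adopting the regimen as a standard if it succeeds.

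**Conclusion.** The point holds as an inexpensive improvement, not as a flaw that invalidates the comparison. The protocol closes its data list without a baseline opioid measure and does not exclude opioid users, so as written the analysis can neither adjust for prior use nor display it by arm.

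The size is unknown. On the stated assumptions (5-20% users, 1.5-2.5 times the need, CV 0.4 within stratum, two-sided 5%, 24 per arm):

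- baseline use explains about 7-52% of the outcome variance;
- adjusting raises power by about 3 to 28 points (68.6% to 71.5% at the mild end, 35.8% to 63.7% at the severe end);
- an imbalance of three or more users occurs in 9-36% of trials, and three extra users in one arm move the difference by about 6-17% of the mean, against a target of 30%.

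If the planning SD came from patients that included opioid users, adjustment adds to the planned power rather than restoring it. In every setting examined, adjustment helps.

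**What to change.** Amend the recording sentence in the Research Plan so that pre-operative opioid use (yes/no, and daily dose in morphine equivalents) is also taken from the chart before randomization. Pre-specify it as a covariate in the comparison of 48-hour narcotic use, and report it by arm. The same amendment can make clear that the allocated arm and the time of discharge are recorded.

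The cost is one or two chart items per patient, slightly more protected health information, and an IRB wording change. Eligibility and sample size do not change.
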